1. LIST OF ACRONYMS AND ABBREVIATIONS

Table 1: List of Acronyms and Abbreviations

Abbreviation	Term
ADA	Anti-Drug Antibody
AE	Adverse Event
AESI	Adverse Event of Special Interest
ATC	Anatomical Therapeutic Chemical
AUC	Area under the drug concentration time curve
BOR	Best Overall Response
CI	Confidence Interval
C _{max}	Maximum concentration
CPS	Combined Positive Score
CR	Complete Response
CTCAE	Common Terminology Criteria for Adverse Events
DCR	Disease Control Rate
DO.R	Duration of Response
EAS	Evaluable Analysis Set
eCRF	electronic Case Report Form
EU	European Union
FAS	Full Analysis Set
HLGT	High-level Group Term
HLT	High-level Term
ICH	International Conference on Harmonization
IERC	Independent Endpoint Review Committee
irAE	Immune-related Adverse Event
IRAE	Infusion-related Adverse Event
ITT	Intention-to-Treat
MedDRA	Medical Dictionary for Regulatory Activities
Msec	Milliseconds
NCI	National Cancer Institute
NEC	Not Elsewhere Classified
ORR	Objective Response Rate
OS	Overall Survival

PD	Progressive Disease
PD-L1	Programmed Death-Ligand 1
PFS	Progression Free Survival
PK	Pharmacokinetic(s)
PP	Per Protocol
PR	Partial Response
PT	Preferred Term
QTc	QT Interval Corrected
RECIST	Response Evaluation Criteria in Solid Tumors
SAP	Statistical Analysis Plan
SD	Stable Disease
SMQ	Standardised MedDRA Queries
SOC	System Organ Class
TCR	Tumor Control Rate
TEAE	Treatment Emergent Adverse Event
ULN	Upper Limit of Normal
USA	United States of America

AMENDMENT FROM PREVIOUS VERSION

- Updated timing of filing analysis cutoff date, to provide minimum 12 months median follow-up and 6-months follow up on objective responses, as requested by FDA.
- Removed from SAP the exploratory analysis of AEs using sponsor broad and narrow definition of immune-mediated AEs — due to FDA request not to use a definition based on use of steroids.
- Divided cluster of immune-mediated Skin Disorders into Rash AEs and Pruritis AEs
- Flattened the hierarchical structure of clusters of immune-mediated AEs
- Specified that clusters of immune-mediated AEs will be evaluated during extended on-treatment period.
- Editorial changes/corrections

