3. STUDY OBJECTIVES AND ENDPOINTS

3.1. PRIMARY OBJECTIVE OF PHASE 2

- To assess the objective response rate (ORR) according to Response Evaluation Criteria in Solid Tumors (RECIST) 1.1, as determined by an Independent Endpoint Review Committee (IERC)

3.2. SECONDARY OBJECTIVES OF PHASE 2

- To assess the safety and tolerability of balstilimab in subjects with metastatic, locally advanced, and/or unresectable cervical cancer
- To characterize the balstilimab pharmacokinetic (PK) profile
- To evaluate the immunogenicity of balstilimab and correlate it to exposure
- To assess ORR according to RECIST 1.1 as determined by investigator
- To assess duration of response (DOR), disease control rate (DCR), duration of stable disease (SD), time to response, and progression-free survival (PFS) time per RECIST 1.1
- To assess overall survival (OS) rate
- To assess OS time

3.3. EXPLORATORY OBJECTIVES OF PHASE 2

- [REDACTED]
- [REDACTED]

- Baseline expression of programmed death-ligand 1 (PD-L1) association with clinical outcomes

3.4. PRIMARY ENDPOINTS OF PHASE 2

- Confirmed ORR per RECIST 1.1, as determined by an IERC, in the analysis population.

Note: The population for primary efficacy analysis, specified in the study protocol, consists of “All subjects in Phase 2 who have received ≥ 1 dose of trial treatment and have measurable disease at baseline, according to the IERC assessment.”

3.5. SECONDARY ENDPOINTS OF PHASE 2

- Frequency, severity, and duration of treatment-emergent adverse events (TEAEs) and laboratory abnormalities, using NCI-CTCAE v4.03
- Balstilimab PK parameters which may include (but are not limited to) maximum drug concentration observed postdose at steady-state ($C_{\max-ss}$), minimum observed concentration at steady-state ($C_{\min-ss}$), area under the drug concentration-time curve within time span t_1 to t_2 at steady-state ($AUC_{(t_1-t_2)-ss}$), area under the drug concentration-

time curve from time zero to time t ($AUC_{(0-t)}$), area under the drug concentration-time curve from time zero to infinity ($AUC_{(0-\infty)}$), time to maximum observed concentration (t_{max}), terminal disposition rate constant (λ_z), terminal elimination half-life ($t_{1/2}$), systemic clearance (CL), and volume of distribution (Vd)

Note: Analysis of PK parameters and correlation with anti-drug antibody concentrations is not covered in this SAP, it will be conducted according to a separate PK analysis plan.

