5.6. HANDLING OF PARTIAL DATES FOR ADVERSE EVENTS

When determining TEAEs, partial dates will be handled as follows.

- If the day of the month is missing, the onset day will be set to the first day of the month unless it is the same month and year as study treatment. In this case, the onset date will be assumed to be the first dose date of treatment.

- If the onset day and month are both missing, the day and month will be assumed to be 1 January, unless the event occurred in the same year as the study treatment. In this case, the event onset will be coded to the first dose date of treatment to conservatively report the event as treatment emergent.
- A missing onset date will be coded as the first dose date of treatment. If the resulting onset date is after a reported date of resolution, the onset date will be set equal to the date of resolution.
- A partially missing resolution date will be conservatively imputed as the latest date in the range of missing date element(s) (for example 2020-10-31 if the date is 2020-10-UNK), date of last dose + 90 days, day of study discontinuation, or death, whichever comes first.

Data listings will present the partial date as recorded in the electronic case report form (eCRF).

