5.10. HANDLING OF MISSING DATA

Missing data will not be imputed, except for:

- Missing date parts, i.e., partial dates, discussed above
- Missing AEs grade severity and relationship to study drug of AEs, discussed in [Section 7.6.2](#)
- Missing efficacy assessments discussed in Section 7.7.

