The analysis of irAEs in the above summaries will be performed using data as reported by investigator (the primary analysis). In addition, as an exploratory analysis, TEAEs using sponsor's broad and narrow definitions of irAEs, will be summarized. For each irAE, the summary will include median time (and range) to onset, median duration (and range) of the first instance of such AE per patient. Finally, descriptive statistics will be provided for time of onset, cycle of onset, and cumulative dose at onset of first irAE of any type.

If an SOC or PT was reported more than once for a subject, the subject would only be counted once in the incidence for that SOC or PT.

In tabulation by severity grade:

- For a given SOC, only the most severe SOC for each subject will be included
- For a given PT, only the most severe PT for each subject will be included

In addition, TEAEs (evaluated within extended treatment period) will be reported for the following clusters of immune-mediated AEs: pneumonitis, colitis and diarrhea, hepatitis, and liver function abnormalities, endocrinopathies, nephritis and renal dysfunction, skin disorders, other immune-related AEs. These clusters will be defined by the following MedDRA version 22.1 Preferred Terms:

- **Pneumonitis:** interstitial lung disease; pneumonitis; acute interstitial pneumonitis; immune-mediated pneumonitis
- **Colitis:** allergic colitis, autoimmune colitis, colitis, colitis erosive, colitis microscopic, enterocolitis hemorrhagic, eosinophilic colitis, necrotizing colitis, neutropenic colitis, enterocolitis, immune-mediated enterocolitis,
- **Diarrhea:** diarrhoea, diarrhoea hemorrhagic
- **Hepatitis:** acute hepatic failure, autoimmune hepatitis, hepatic failure, hepatitis, hepatitis acute, hepatotoxicity, liver injury, hepatocellular injury, immune-mediated hepatitis, immune-mediated hepatic disorder, drug-induced liver injury
- **Hypothyroidism:** autoimmune hypothyroidism, hypothyroid goiter, hypothyroidism, immune-mediated hypothyroidism, myxoedema, thyroid atrophy
- **Hyperthyroidism:** Basedow's disease, hyperthyroidism, Marine Lenhart syndrome, primary hyperthyroidism, immune-mediated hyperthyroidism, secondary hyperthyroidism, tertiary hyperthyroidism, thyroid dermatopathy, thyroid crisis, thyrotoxic periodic paralysis, toxic goiter, toxic nodular goiter,

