The median duration of TEAE (in days) will be calculated using Kaplan Meier analysis for all patients and AE included in a cluster. Unresolved AEs or AEs with missing resolution information and date will be treated as censored data with the end of extended on-treatment period as censoring date.

Death summary table will present reasons for deaths on treatment period, in survival follow-up, and overall.

Death details will also be listed (if applicable) including:

- Number of doses of balstilimab
- Number of cycles

- Age at death
- Study days relative to first dose date, calculated as (death date – first dose date + 1)
- Number of days to death from last dose, calculated as (death date – last dose date + 1)
- Precipitating AE (if death is an outcome of AE)
- Immune-related AE (if death is an outcome of irAE per investigator)
- Cause of deaths

The following listings will be provided in Safety Analysis Set:

- All AEs (with TEAEs flagged)
- Related TEAEs
- Serious TEAEs
- TEAEs leading to treatment discontinuation
- TEAEs leading to death
- Death details (including age, study day, and days from last dose, AEs, and death cause).

Adverse events observed between signing the informed consent and first dose of study drug will be listed with negative study days.

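### SAP 7.6.2 gives irAE duration as a median and range with no estimator or rule for ongoing events; if some irAEs are unresolved, the natural reading makes the medians too short

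*SAP*

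**What the plan says.** Duration of AEs is part of a Phase 2 secondary endpoint. SAP 3.5 lists "Frequency, severity, and duration of treatment-emergent adverse events (TEAEs) and laboratory abnormalities, using NCI-CTCAE v4.03".

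SAP 7.6.2 treats duration in two places.

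- **irAE summary.** After stating that irAE summaries use investigator-reported data, the section asks, for each irAE, for the "median duration (and range) of the first instance of such AE per patient". No estimator is named and ongoing events are not mentioned.
- **Cluster summary.** For the predefined Preferred Term clusters, "The median duration of TEAE (in days) will be calculated using Kaplan Meier analysis for all patients and AE included in a cluster". The next sentence adds: "Unresolved AEs or AEs with missing resolution information and date will be treated as censored data with the end of extended on-treatment period", which serves as the censoring date. The cluster tables also give the percent resolved.

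The general rules are these.

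- SAP 7.2 sets the default for continuous variables: number of subjects, mean, standard deviation, median, minimum and maximum.
- SAP 5.6 says "A partially missing resolution date will be conservatively imputed as the latest date in the range of missing date element(s", subject to several caps. This concerns dates that are partly recorded, not events without an end.
- SAP 5.10 opens "Missing data will not be imputed, except for" and then lists partial dates, AE severity and relationship, and efficacy assessments.

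The SAP's list of amendments also says: "Removed from SAP the exploratory analysis of AEs using sponsor broad and narrow definition of immune-mediated AEs". A sentence announcing that analysis still stands in 7.6.2, directly before the irAE duration sentence.

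**The concern.** A duration is a time-to-event quantity. An event that has not ended by the cutoff carries information (it lasted at least this long), and a plain median has no way to use it. If such events are left out, the longest durations go first and irAEs look shorter than they are.

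Unresolved irAEs are foreseeable here. The BLA Filing analysis uses a fixed cutoff of 11 Feb 2021 (SAP 4.2). Protocol Table 8 anticipates continuing corticosteroids for some subjects with adrenal insufficiency. Protocol 6.3.3.2 lets follow-up of an adverse drug reaction end when the event becomes stable, not only when it resolves.

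The two halves of SAP 7.6.2 could also disagree about the same event: censored in the cluster table, absent from the irAE table.

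**Working it through.** The plan states no figure for irAE duration, so there is none to reproduce. The check has a textual part, an illustration of size, and a look at the censoring date.

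**1. Does any stated rule reach an unresolved irAE outside the cluster tables?**

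| Rule | Reaches it? |
|---|---|
| SAP 7.2, default descriptive statistics | Gives median and range; needs a completed duration |
| SAP 5.6, resolution dates | Partly missing dates only |
| SAP 5.10, missing data | Adds nothing for an ongoing event |
| SAP 7.6.2, Kaplan-Meier and censoring | Tied to AEs included in a cluster |

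Elsewhere the SAP names Kaplan-Meier where it intends it: DOR (7.7.3), PFS (7.7.9) and OS (7.7.10). A plain median is therefore the natural reading of the irAE sentence.

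**2. Size under common follow-up.** Assumptions, none from the documents: exponential durations with rate λ, the same follow-up for every event, fraction f unresolved. The resolved-only median m satisfies 1 − exp(−λm) = 0.5(1 − f). The true median is ln 2/λ. Hence

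ratio = −ln(1 − 0.5(1 − f)) / ln 2.

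- f = 0.2: −ln(0.6)/ln 2 = 0.511/0.693 = 0.74
- f = 0.4: −ln(0.7)/ln 2 = 0.357/0.693 = 0.51
- f = 0.6: −ln(0.8)/ln 2 = 0.223/0.693 = 0.32; here the true median lies beyond follow-up, so Kaplan-Meier would report it as not reached

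**3. Size under varying follow-up.** Assume exponential durations with median 60 days and exponential censoring at rate μ. The unresolved share is q = μ/(λ + μ), so λ + μ = λ/(1 − q). Resolved times, and all observed times, then have median 60(1 − q): 48, 36 and 24 days at q = 0.2, 0.4 and 0.6. A simulation of 200,000 events per scenario agreed (47.9, 35.8 and 24.1 days for resolved events), and Kaplan-Meier returned about 60 days throughout.

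**4. Some events never resolve.** Assume a fraction never resolves, the rest have median 30 days, and follow-up is uniform over 90 to 400 days (simulated).

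| Never resolve | Dropped | Counted at follow-up time | Kaplan-Meier |
|---|---|---|---|
| 20% | 29 days | 43 | 43 |
| 30% | 29 days | 54 | 54 |
| 40% | 29 days | 78 | 78 |
| 60% | 29 days | 148 | not reached |

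How unresolved events are handled therefore matters. Dropping them shortened the median in every scenario. Keeping them at their follow-up time gave the right median in the 20% to 40% rows here, but not in step 3.

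**5. The cluster censoring date.** SAP 5.4 ends the extended on-treatment period 90 days after the last dose, or at end of study if earlier. For a subject dosed on the cutoff date, 11 Feb 2021 + 90 days = 12 May 2021. Unless end of study comes first, any last dose after 13 Nov 2020 puts the censoring date beyond the cutoff, crediting time that was not observed.

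**The case against.** The best defence is that the SAP nowhere says unresolved irAEs are dropped. It is silent on the estimator. Censoring is not imputation, so SAP 5.10 does not itself exclude an ongoing event. The censoring sentence is generally worded, irAEs count as TEAEs, and a programmer might apply it to both tables. It stands that a resolved-only median is an inference, not a stated rule. But the censoring sentence sits in the cluster paragraph, directly after a sentence limited to clusters, and nothing carries it over to the irAE summary.

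A reader might infer three stronger things that the documents do not support.

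- *That duration is the SAP's primary irAE analysis.* The words "The analysis of irAEs in the above summaries will be performed using data as reported by investigator (the primary analysis" (closing bracket omitted) label the data source for the incidence tables above them. None of those reports duration.
- *That persistent endocrinopathies would be hidden.* Thyroid disorders, pituitary-adrenal insufficiency and diabetes are clusters, with Kaplan-Meier durations and percent resolved. All AEs are also listed individually.
- *That a bias of known size has been shown.* The unresolved share and the duration distribution are both assumed.

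What remains is narrower. Clusters are fixed term lists. Protocol 5.6 names arthritis, glomerulonephritis and cardiomyopathy as potential irAEs, and none is a listed term (only rheumatoid arthritis and myocarditis are near them). Such events would get a summarised duration only through the irAE sentence. The clusters also pool all AEs, whereas the irAE summary takes the first instance per patient, so one does not replace the other.

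The scope of the duration sentence is also slightly unclear, because it follows the sponsor-definition sentence. If it belonged only to that removed analysis, investigator-reported irAEs would have no specified duration summary, which would also be a gap.

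**Conclusion.** The point holds in conditional form. On its natural reading, SAP 7.6.2 gives an unresolved irAE no place in the duration summary, and the medians are short if some irAEs are unresolved. Under common follow-up and exponential durations, the resolved-only median is 0.74, 0.51 and 0.32 of the truth at 20%, 40% and 60% unresolved; under varying follow-up it is 0.80, 0.60 and 0.40. These are illustrations, and the trial's own figure cannot be derived from the documents. If ongoing events were instead kept at their follow-up time, the median could be unaffected, but the upper end of the range would still be understated.

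The practical weight falls on irAEs outside the cluster lists and on agreement between the two sets of tables. This is a descriptive part of a secondary safety endpoint in a single-arm study without formal hypothesis testing, and it does not touch the response-rate analysis. The change is still worth making, because the SAP already uses the better method a few paragraphs later.

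**What to change.** In SAP 7.6.2:

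1. Estimate the duration of the first instance of each investigator-reported irAE by Kaplan-Meier, with unresolved events censored. Show the number and percent unresolved beside the median.
2. Use one censoring date for the irAE and cluster tables: the last date on which the event's status is known, and no later than the data cutoff. The cluster paragraph must be changed too, or two conventions will remain.
3. Delete the remaining sentence on the sponsor's broad and narrow irAE definitions, so that the duration sentence plainly applies to investigator-reported irAEs.

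The cost is a few sentences and a modest adaptation of the cluster program, which now takes all AEs in a cluster rather than the first instance per patient and uses a different censoring date. Some irAE medians will be longer or not reached, and the cluster medians may shift with the new censoring date.

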**Table 7: Hepatic Immune-related Adverse Event Management Algorithm**

Hepatic Immune-related Adverse Events		
Grade of Liver Test Elevation (NCI CTCAE v4.03)	Management	Follow-Up
Grade 1 AST or ALT >ULN to 3 x ULN and/or total bilirubin >ULN to 1.5 x ULN.	
 
Continue AGEN2034 therapy per protocol.
 
	
 
Continue liver function tests (LFT) monitoring per protocol.
 
If worsens: treat as Grade 2 or Grade 3–4.
 

Grade 2 AST or ALT >3 to ≤5 x ULN and/or total bilirubin >1.5 to ≤3 x ULN.	
 
Delay AGEN2034 therapy per protocol.
 
Increase frequency of monitoring to every 3 days.
 
If subject has concurrent AST or ALT > 3 x ULN AND total bilirubin > 2 x ULN, Discontinue AGEN2034 therapy per protocol.
 
	
 
If returns to baseline: resume routine monitoring; resume AGEN2034 therapy per protocol.
 
If elevations persist >5 to 7 days or worsen: 0.5–1 mg/kg/day methylprednisolone IV or oral equivalent. When LFT returns to Grade 1 or baseline, taper corticosteroids over at least 1 month, consider prophylactic antibiotics for opportunistic infections, and resume AGEN2034 therapy per protocol.
 

Grade 3–4 AST or ALT >5 x ULN and/or total bilirubin >3 x ULN.	
 
Discontinue AGEN2034 therapy per protocol.
 
Increase frequency of monitoring to every 1–2 days.
 
1–2 mg/kg/day methylprednisolone IV or oral equivalent*.
 
Add prophylactic antibiotics for opportunistic infections.
 
Consult gastroenterology.
 
Consider obtaining MRI/CT scan of liver and liver biopsy if clinically warranted.
 
	
 
If returns to Grade 2: taper corticosteroids over at least 1 month.
 
If does not improve in > 3 to 5 days, worsens or rebounds: add mycophenolate mofetil 1 g twice daily. If no response within an additional 3–5 days, consider other immunosuppressants per local guidelines.
 

\*The recommended starting dose for Grade 4 hepatitis is 2 mg/kg/day methylprednisolone IV.

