**Table 9: Renal Immune-related Adverse Event Management Algorithm**

Renal Immune-related Adverse Events		
Grade of Creatinine Elevation (NCI CTCAE v4.03)	Management	Follow-Up
Grade 1 Creatinine > upper limit of normal (ULN) and > than baseline but $\leq$ 1.5x baseline.	
 
Continue AGEN2034 therapy per protocol.
 
Monitor creatinine weekly
 
	
 
If returns to baseline: resume routine creatinine monitoring per protocol.
 
If worsens: treat as Grade 2 or Grade 3-4.
 

Grade 2-3 Creatinine > 1.5x baseline to $\leq$ 6x ULN.	
 
Delay AGEN2034 therapy per protocol.
 
Monitor creatinine every 2-3 days
 
0.5 to 1.0 mg/kg/day methylprednisolone IV or oral equivalent.
 
Consider renal biopsy
 
	
 
If returns to Grade 1: taper corticosteroids over at least 1 month, consider prophylactic antibiotics for opportunistic infections, and resume AGEN2034 therapy and routine creatinine monitoring per protocol.
 
If elevations persist <math>></math> 7 days or worsen: treat as Grade 4.
 

Grade 4 Creatinine > 6x ULN.	
 
Discontinue AGEN2034 therapy per protocol.
 
Monitor creatinine daily.
 
1.0 to 2.0 mg/kg/day methylprednisolone IV or IV equivalent.
 
Consult nephrologist.
 
Consider renal biopsy
 
	
 
If returns to Grade 1: taper corticosteroids over at least 1 month and add prophylactic antibiotics for opportunistic infections.
 

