### **7.1.2. Abnormal Laboratory Findings and Other Abnormal Investigational Findings**

Abnormal laboratory findings and other abnormal investigational findings (e.g., on an ECG trace) should not be reported as AEs unless they are associated with clinical signs and symptoms, lead to treatment discontinuation, or are considered otherwise medically important by the investigator. If an abnormality fulfills these criteria, the identified medical condition (e.g., anemia, increased ALT) must be reported as the AE rather than the abnormal value itself.

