- **Thyroiditis:** autoimmune thyroiditis, thyroiditis, thyroid acute, thyroiditis chronic, thyroiditis fibrous chronic, thyroiditis subacute, immune-mediated thyroiditis

- **Neuroendocrine Disorders (Pituitary-Adrenal insufficiency):** Addison's disease, adrenal androgen deficiency, adrenal insufficiency, adrenal suppression, adrenocortical insufficiency acute, glucocorticoid deficiency, hypoaldosteronism, mineralocorticoid deficiency, hypophysitis, lymphocytic hypophysitis, hypopituitarism
- **Diabetes** without prior history: type 1 diabetes mellitus, diabetes mellitus, latent autoimmune diabetes in adults, diabetic ketoacidosis.
- **Nephritis:** autoimmune nephritis, lupus nephritis, nephritis, nephritis hemorrhagic, immune-mediated nephritis
- **Rash:** pemphigoid, rash, rash erythematous, rash generalized, rash macular, rash maculopapular, rash pruritic, rash papular, immune-mediated dermatitis
- **Pruritus:** pruritus, pruritus allergic, pruritus generalized

Other Immune-related AEs: myocarditis, immune-mediated myocarditis, uveitis, immune-mediated uveitis, iritis, vitiligo, psoriasis, myositis, immune-mediated myositis, rheumatoid arthritis, systemic inflammatory response syndrome, sarcoidosis, autoimmune disorder, meningitis, encephalitis, encephalitis autoimmune, immune-mediated encephalitis, encephalopathy, autoimmune encephalopathy, immune-mediated encephalopathy, Guillain-Barre syndrome, myasthenia gravis, demyelination, stomatitis, pancreatitis, autoimmune pancreatitis, pancreatitis acute, immune-mediated pancreatitis, immune-mediated gastritis, lichen planus, colitis ulcerative, Crohn's disease, inflammatory bowel disease, hemolytic anemia, immune-thrombocytopenia, immune thrombocytopenic purpura, aplastic anemia, bacytopenia, pancytopenia, immune-mediated pancytopenia

For each cluster, the analysis will summarize: the total incidence and number of all TEAEs included in the cluster and by severity grade, % of pts who received treatment with pituitary and hypothalamic hormones and analogues, with corticosteroids for systemic use, or with thyroid therapy (concomitant medications in, respectively, H01, H02 and H03 ATC2 groups indicated for AE and started following AE onset but no later than the date of AE resolution or 21 days from AE onset, whichever comes earlier), % leading to dose hold, % leading to drug discontinuation, % resolved, time to onset of first TEAE and duration of all TEAEs and TEAEs of grade ≥ 3 .

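### The SAP announces immune-mediated clusters for liver function abnormalities and renal dysfunction but lists no liver-test or renal dysfunction terms, so such events drop out of the cluster-only safety summaries

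*SAP*

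**What the plan says.** SAP 7.6.2 plans a summary of treatment-emergent adverse events (TEAEs) by cluster of immune-mediated events, evaluated over the extended on-treatment period. Its introductory sentence names the clusters, among them "hepatitis, and liver function abnormalities, endocrinopathies, nephritis and renal dysfunction". It then makes the lists that follow the definition: "These clusters will be defined by the following MedDRA version 22.1 Preferred Terms".

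The hepatic bullet is headed Hepatitis. It opens "acute hepatic failure, autoimmune hepatitis, hepatic failure, hepatitis, hepatitis acute, hepatotoxicity, liver injury, hepatocellular injury" and ends with immune-mediated hepatitis, immune-mediated hepatic disorder and drug-induced liver injury. The renal bullet is headed Nephritis and reads in full "autoimmune nephritis, lupus nephritis, nephritis, nephritis hemorrhagic, immune-mediated nephritis".

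For each cluster the SAP asks for incidence and grade, use of systemic corticosteroids and hormone therapies, the percentages leading to dose hold and to discontinuation, the percentage resolved, time to first onset, and duration of all events and of those of grade 3 or higher.

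The protocol describes hepatic and renal immune-related events through laboratory values. Table 7 is organised by "Grade of Liver Test Elevation (NCI CTCAE v4.03" and Table 9 by "Grade of Creatinine Elevation (NCI CTCAE v4.03". Protocol 7.1.2 makes an abnormal laboratory finding an adverse event only if it comes with signs or symptoms, leads to treatment discontinuation, or is judged medically important. When it qualifies, "the identified medical condition (e.g., anemia, increased ALT) must be reported as the AE rather than the abnormal value itself".

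**The concern.** The announced scope and the operative definition disagree. A programmer who follows the term lists will produce hepatic and renal rows without the liver function abnormalities and renal dysfunction that the plan says are covered. A reader who relies on the introductory sentence will assume those events were counted and found to be few.

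The cluster table is where the SAP assembles, organ by organ, how immune-mediated events were managed and how they ended. It also does not depend on the investigator's immune attribution. An event left out of it can be found elsewhere as a count, but not with its steroid use, dose holds and resolution summarised by organ.

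**Working it through.** No sample size, power or event count is involved, so this is a check of text against text.

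**Step 1. Match each announced name to the lists in SAP 7.6.2.**

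| Announced | Term lists supplied |
|---|---|
| Pneumonitis | Pneumonitis |
| Colitis and diarrhea | Colitis; Diarrhea |
| Hepatitis | Hepatitis (11 terms) |
| Liver function abnormalities | None |
| Endocrinopathies | Hypothyroidism; Hyperthyroidism; Thyroiditis; Neuroendocrine; Diabetes |
| Nephritis | Nephritis (5 terms) |
| Renal dysfunction | None |
| Skin disorders | Rash; Pruritus |
| Other | Other (40 terms) |

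Every other name, single or compound, is populated. Only these two are empty, which suggests omission rather than choice.

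**Step 2. Search the hepatic, renal and other lists.** The search strings were increased, abnormal, transaminase, aminotransferase, bilirubin, function, enzyme, creatinine, renal and kidney.

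- Hepatitis: 0 matches in 11 terms. The list does go beyond hepatitis: it has two failure terms (acute hepatic failure, hepatic failure), hepatotoxicity and several liver injury terms.
- Nephritis: 0 matches in 5 terms, and no failure term.
- Other: 0 matches in 40 terms, so it does not catch what the first two miss.

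**Step 3. Ask whether the missing terms are likely to occur.** Table 7 defines its highest hepatic category (grades 3 and 4) as "AST or ALT >5 x ULN and/or total bilirubin >3 x ULN". Table 9 grades renal events by creatinine alone. Protocol 7.1.2 uses increased ALT as its example of a reportable event. Protocol 1.1.2.2 treats nivolumab as the best guide to this drug's safety. Among nivolumab's most frequent severe or serious reactions, Protocol 1.1.3.1 names increased ALT, AST and bilirubin and acute kidney injury, but neither hepatitis nor nephritis. Protocol 1.1.3.2 does name hepatitis, nephritis and renal dysfunction among the common immune-mediated reactions. Coding to the missing terms is therefore plausible, but the documents do not say how often it happens.

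**Step 4. Find which outputs exist only by cluster.**

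| Output | Available without the clusters? |
|---|---|
| Incidence and grade | Yes: investigator-reported irAE tables, any preferred term |
| Time to onset | Yes: irAE summary |
| Duration | First instance per patient only: irAE summary |
| Discontinuation | Yes: TEAE tables by preferred term |
| Laboratory grade and shift | Yes: SAP 7.6.4 |
| Systemic steroid use, dose hold, percent resolved | No |
| Duration of all events and of grade 3 or higher | No |

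**Step 5. Size.** Let N be the subjects with any hepatic TEAE, on listed or unlisted terms, and m those whose hepatic TEAEs are all on unlisted terms. The cluster reports (N − m)/N of the subjects concerned. A subject with both hepatitis and raised ALT is already in the cluster and does not count towards m. The documents give neither N nor m, for the liver or the kidney, so the ratio cannot be evaluated.

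**The case against.** The strongest reply is that little is lost. The clusters are an additional tabulation. SAP 7.6.2 makes investigator-reported irAEs the primary analysis, and any event that the investigator suspects is immune-mediated is an event of special interest, whatever its preferred term. An irAE coded to raised ALT or acute kidney injury is counted there with its grade, onset and first-event duration. Liver tests are further covered by the laboratory-based hepatic event of special interest, the summary of elevations to at least twice the upper limit of normal, and the eDISH plot. Creatinine has its own CTCAE grades and shift table. All of this stands, and it limits the point to the cluster-only outputs.

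Tables 7 and 9 are management algorithms, not coding rules, so an event graded by ALT or creatinine may still be reported as hepatitis or nephritis. Protocol 7.1.2 also keeps many laboratory changes from becoming adverse events at all. Both points stand. They reduce the number of events at issue but do not fill the empty clusters.

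Finally, clusters count TEAEs without an attribution filter, so laboratory terms would bring in non-immune events. Protocol 7.1.7 records signs and symptoms of progression as adverse events, and Protocol 5.6.4 and 5.6.6 ask that non-inflammatory causes be ruled out first. This is a real cost, but the SAP already accepts it by listing diarrhoea, stomatitis, pancytopenia and hepatic failure. It argues for separate rows, not for leaving the names without terms.

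A reader might infer that hepatic and renal immune toxicity is undercounted across the trial, or that the hepatic cluster holds hepatitis terms alone. The documents support neither. The primary irAE tables do not use these lists, and the hepatic list includes failure, hepatotoxicity and liver injury terms.

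**Conclusion.** The mismatch is certain on the face of SAP 7.6.2. It is complete for renal dysfunction, where no term is listed. For the liver it is confined to liver-test terms. The consequence is limited: qualifying events coded to those terms are missing from the cluster rows, and so from the only planned per-organ summaries of steroid use, dose hold, percent resolved, and duration of all and of grade 3 or higher events. The primary irAE analysis, discontinuation by preferred term and laboratory reporting are unaffected.

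The size of the shortfall is unknown. Any percentage, or any statement that laboratory-coded events are the commonest form of this toxicity, would go beyond the documents. The conclusion assumes only that some TEAEs will be coded to the unlisted terms, which the protocol's grading tables and its own reporting example make plausible. The point should be corrected, but it does not threaten the trial's main safety conclusions.

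**What to change.** Before the database is available for analysis, add two flattened clusters to SAP 7.6.2:

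- **Liver function abnormalities:** terms for increased ALT, AST, transaminases, hepatic enzymes, liver function test and blood bilirubin.
- **Renal dysfunction:** blood creatinine increased, acute kidney injury, renal failure and renal impairment.

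The exact term names should be checked against MedDRA 22.1. Leave the Hepatitis and Nephritis rows as they are, so that the specific counts stay visible, just as Diarrhea already sits beside Colitis. State in the label of each new row that it counts TEAEs regardless of attribution, and show the number that the investigator called immune-related alongside.

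The cost is an edit to the term list and two more rows of output. Design and data collection do not change. The new rows will include some non-immune events, for example from disease progression, which is why the label and the parallel count are needed. If the sponsor intends the narrower scope, the minimum repair is to rename the clusters hepatitis and nephritis and state where laboratory-coded toxicity is reported. That removes the contradiction, but still leaves those events without the cluster-only summaries.
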